6.2.1 LIST OF METHODS AND PRESENTATION

A table with each feasibility criterion will be reported, alongside the percentage or nominal value for each of the sub-categories.

Means, medians, standard deviations, (empirical) 95% confidence intervals and ranges will be reported for continuous covariates, while for their respective binary transformations, we will report frequencies and percentages.

The impact of each lifestyle factor of interest (namely sleep, diet, physical activity) will be estimated as a causal treatment effect (e.g. ATE or ATT) (Markoulidakis, Taiyari, et al., 2021) using the doubly robust model. PS and balancing weights (assuming the availability of a large enough sample size, and that adequate balance is achieved – this is defined as the maximum KS statistic of all balancing covariates being below or equal to 0.1) will be used to control for confounding bias. The covariates which will be used to control for confounding bias are the lifestyle factors not under study in each case (e.g., when modelling the effect of sleep on the progression of cUHDRS, then diet and physical activity will be considered as confounders), as well as the baseline value of cUHDRS. If sample size allows, additional covariates will be added to control for confounding bias, including age and HD stage. If adequate balance is not achieved at baseline (defined as maximum KS statistic below or equal to 0.1), then mean differences of the outcome will be reported, and/or estimates using a regression model adjusting for the other two lifestyle factors, age, and HD stage. In the latter case, no balancing weights will be used. The full analysis will be re-attempted using the four components of cUHDRS as outcome variables, and similar results as for the original analysis will be reported.

TPL/008/2(v1.0)

DOMINO-HD: STATISTICAL ANALYSIS PLAN

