6. ANALYSIS

6.1 OUTCOME DEFINITIONS

6.1.1 PRIMARY OUTCOME(S)

The primary objective of this study is to establish the feasibility of linking lifestyle, clinical and genetic data and to explore their interplay with HD symptoms and severity.

We will explore the proportions of recruited participants with linked DOMINO-HD and Enroll-HD clinical data as well as linked GWAS data. We will also explore follow-up rates and lifestyle and wearable activity tracker data completeness and balance statistics in important variables. Our data will be used to provide progression criteria recommendations for future studies in this field.

Aspects of feasibility which will be assessed are:

- Completeness of key lifestyle questionnaires (at baseline: HD Pro-Triad, FFQ, LTPA, Sleep, IPAQ, Relationship) data [>80% returned with >80% completeness = feasible, >60% returned with >60% completeness = changes required, <60% returned or <60% completeness = not feasible]
- Completeness of activity tracker data [>70% feasible, 50-70% changes required, <50% not feasible]
- % participants linked with Enroll-HD clinical data [>80% feasible, 60-80% changes required, <60% not feasible]
- % participants linked with GWAS data [>60% feasible, 40-60% changes required, <40% not feasible]
- % participants with follow-up at 12m [>70% feasible, 50-70% changes required, <50% not feasible]
- Feasibility of balancing important covariates. Adequate balance of baseline covariates is achieved when the maximum Kolmogorov-Smirnov (KS) value is equal to or below 0.1. However, as the recommendation is for 60-80 observations per covariate per treatment

TPL/008/2(v1.0)

Centre for Trials Research Canolfan

Ymchwil Treialon

DOMINO-HD: STATISTICAL ANALYSIS PLAN

group (Markoulidakis, Holmans, et al., 2021), the feasibility of achieving balance should be determined alongside the available sample size.

• Agreement between questionnaire and activity tracker data

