6.2.2 COVARIATE ADJUSTMENT

Unweighted analyses (using regression models) will control for age, HD stage, as well as baseline values for the outcomes. Additionally, we will control for the two lifestyle (the continuous version of these) factors not included in each case.

The primary goal is to control for confounding bias, using PS and balancing weights (Markoulidakis, Taiyari, et al., 2021), for the two lifestyle factors other than the one under study in each case. Expecting limitations due to the restricted sample size (Markoulidakis, Holmans, et al., 2021), we will attempt to balance additionally for age, HD stage, and baseline values of the outcome.

The outcome analysis will also be performed using the LifeHD score constructed, as a categorical covariate, with and without the use of PS and balancing weights. The LifeHD score will be used both in addition to the individual lifestyle factors (e.g. using LifeHD score as 'treatment', and the three lifestyle factors as confounders), and solely – without taking into consideration the other lifestyle factors.

Outcome will be standardised, so that we report standardised effect sizes. The estimand of interest (e.g. ATE or ATT) will be determined based on whether adequate balance is achieved or not. If we are unable to achieve adequate balance, then unweighted regression and means difference will be reported.

Additionally, significance tests for difference of means of the covariates we wish to control for and the outcome will be reported. The pseudo-groups will be created using the binary indicators of diet, sleep, and physical activity.

Genetic information (via polygenic risk scores) will only be used in the analysis if it is feasible based on the available sample.

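### The KS ≤ 0.1 balance rule covers only covariates placed in the weights, so a weighted effect can be called balanced with age and HD stage in neither the weights nor the outcome model

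*SAP*

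**What the plan says.** Section 6.2.1 estimates the effect of sleep, diet and physical activity with a doubly robust model. Weights are used if the sample is large enough and balance is adequate; "this is defined as the maximum KS statistic of all balancing covariates being below or equal to 0.1".

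On the balancing set, 6.2.1 says: "The covariates which will be used to control for confounding bias are the lifestyle factors not under study in each case", "as well as the baseline value of cUHDRS". It then adds: "If sample size allows, additional covariates will be added to control for confounding bias, including age and HD stage". No number defines when the sample allows this.

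Section 6.2.2 draws the line elsewhere. Its primary goal is the two other lifestyle factors; beyond those, "we will attempt to balance additionally for age, HD stage, and baseline values of the outcome". Baseline outcome is thus core in 6.2.1 and an attempt in 6.2.2.

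If balance fails, 6.2.1 reports mean differences and/or "estimates using a regression model adjusting for the other two lifestyle factors, age, and HD stage". Section 6.2.2 states: "Unweighted analyses (using regression models) will control for age, HD stage, as well as baseline values for the outcomes", together with the two other lifestyle factors.

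Section 6.1.1 makes balance a primary feasibility aspect with the same 0.1 limit, lists no covariates, and notes that "the recommendation is for 60-80 observations per covariate per treatment" group.

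**The concern.** The rule takes a maximum over whichever covariates were chosen, so leaving out a covariate that is hard to balance makes it easier to pass. Age and HD stage plausibly relate both to sleep or step count and to 12-month cUHDRS, and both are measured. The plan adjusts for them in the fallback regression, in the first step of the LifeHD score (Appendix C) and in the wear-time regression (6.4). Only the preferred causal analysis leaves them optional.

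Two results are at stake: a lifestyle effect labelled causal and balanced that partly reflects age and stage, and a feasibility statement that balance was achieved without saying for what.

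**Working it through.** **1. Covariate sets side by side**

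| Analysis | Two other lifestyle factors | Baseline outcome | Age, HD stage |
|---|---|---|---|
| Weights, 6.2.1 | yes | yes | if sample allows |
| Weights, 6.2.2 | yes | attempt | attempt |
| Fallback regression, 6.2.1 | yes | not named | yes |
| Fallback regression, 6.2.2 | yes | yes | yes |
| Outcome part of doubly robust model | no separate list | no separate list | no separate list |

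Under 6.2.2 the weighted minimum (two covariates) is a strict subset of the fallback regression (five). Under 6.2.1 alone neither set contains the other: the weights have baseline cUHDRS, the regression has age and stage.

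**2. What the sizing recommendation supports**

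Inputs: 60-80 per covariate per group (6.1.1); N = 300-450 (3.3); tertile split for sleep (6.2). Required group size = covariates × 60 to 80.

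- Five covariates: 5 × 60 = 300 to 5 × 80 = 400 per group.
- Three covariates: 180 to 240 per group.
- Smaller group at a tertile split: 300/3 = 100 to 450/3 = 150. This supports 100/80 = 1.25 to 100/60 = 1.7 covariates at N = 300, and 1.9 to 2.5 at N = 450.
- Smaller group at a median split, the largest that any two-way cut can give: 150 to 225. This supports 1.9 to 2.5 covariates at N = 300, and 2.8 to 3.75 at N = 450.

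Five covariates are not supported at any planned N or cut. Three are supported only near N = 450 with a near-equal split (225 against 180), and then only at the lower figure of 60.

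**3. How often a pass hides imbalance**

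Three simulations used a tertile exposure at N = 300, with weights on two lifestyle factors plus baseline cUHDRS. All associations are assumptions, and each cell follows the order of the dependence column. A and B use entropy balancing on means and variances with no true lifestyle effect; C uses logistic propensity weights and looks at balance only.

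| Simulation | Dependence of exposure on age and severity | Rule passed | Passes with hidden KS > 0.1 |
|---|---|---|---|
| A, 400 runs | coefficient 0.1 / 0.2 / 0.3 | 66 / 62 / 48% | age or stage: 75 / 98% (first two settings) |
| B, 300 runs | coefficient 0.1 / 0.2 / 0.3 | 59 / 53 / 46% | age or stage: 77 / 97 / 100% |
| C, 1000 runs | log-odds 0.3 / 0.5 / 0.8 for age, half that for severity | 45 / 36 / 33% | age: 93 / 99.7 / 100%; both: 28 / 51 / 87% |

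With all five covariates weighted, 51/37/23% pass in A and 45/34/23% in B.

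Chance alone accounts for part of this. With no association, no weighting and a 100 v 200 split, KS exceeds 0.1 in about 47% of samples for one continuous covariate and in about 52% for age or a correlated four-level stage. In C, with no direct dependence on age or severity, age exceeds 0.1 in 52% of passes at N = 300 and 27% at N = 450.

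**4. False effect among passing runs (A and B)**

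- Three covariates weighted: 0.04-0.12 SD in A (0.08 at coefficient 0.2); 0.02/0.05/0.06 SD in B.
- Two lifestyle factors only (the 6.2.2 minimum): 0.15-0.46 SD in A; 0.17/0.30/0.44 SD in B.
- Age, HD stage and baseline outcome added to the outcome model: about 0.01 SD.

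**The case against.** Much of the case on the other side stands.

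- **A reader might infer that the plan, followed as written, must omit age and stage.** It does not say so. Section 6.2.2 commits to attempting them, and 60-80 is a recommendation to be read with the sample size. Applied as a hard rule it would also exclude the three core covariates at a tertile split, which points to no weighting rather than to weighting without age and stage.
- **A reader might infer that passing the rule always gives weaker confounding control than failing it.** That follows only from the 6.2.2 minimum. Under 6.2.1 the sets are not nested, and mean differences alone are permitted after a failure.
- **A reader might set the two-covariate bias (about 0.3 SD at coefficient 0.2) against the 0.23 detectable effect in section 3.3.** That comparison is not valid: 0.23 is per unit of a continuous predictor, the bias is a two-group contrast, and the two-covariate set drops the baseline cUHDRS that 6.2.1 lists unconditionally.
- **A reader might infer that any failed KS can be blamed on sample size.** Three covariates with 225 per group meet the lower figure of 180.
- **Other checks exist.** Section 6.2.2 plans tests on the covariates to be controlled for, 6.2.3 checks overlap, and 6.2.3 and 6.2.5 use OVtool or E-values. These may reveal imbalance, but none feeds the balance rule. The unmeasured-confounding tools also do not replace adjustment for variables already collected.
- **A doubly robust outcome model could contain age and stage.** It could, and the bias would then nearly vanish. The plan does not say that it will.

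The effect estimates are also secondary and exploratory, which limits the consequences.

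**Conclusion.** The point holds on the text. The rule is judged on an unfixed set, age and HD stage are optional in that set, and nothing requires them in the outcome model or requires their KS when they are left out. The two sections also disagree on whether baseline outcome is core.

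With baseline cUHDRS weighted, the likely bias is modest, roughly 0.02-0.12 SD; it is larger if baseline is not weighted. Both depend on assumed associations and on an outcome model limited to the weighted covariates. Hidden imbalance appeared in all three simulations, but at weak dependence much of it is chance at 100 v 200. The arithmetic in step 2 needs no assumption beyond the plan's own figures. This should be corrected; it does not invalidate the study.

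**What to change.** 1. In 6.2.1 and 6.2.2, always include age, HD stage and the baseline outcome, with the two other lifestyle factors, in the outcome regression of the doubly robust model and in the fallback regression, whether or not they are in the weights. Make the two sections agree on baseline outcome.
2. Always compute and report weighted KS for all five covariates. In 6.1.1, state the balance result together with the set it covers, so that balance is not claimed for age or HD stage when its KS exceeds 0.1.
3. Do not let the five-covariate KS block a weighted analysis that balances fewer. In simulation A at coefficient 0.2, judging five while weighting three would pass in about 0.62 × 0.02 ≈ 1% of runs.

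The cost is wording. The variables are collected and the planned software already computes KS. The outcome model gains up to five degrees of freedom over one with only the two lifestyle factors (age 1, four-level stage 3, baseline 1), and the balance statement will be less favourable.

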3.3 SAMPLE SIZE

Based on previous clinical trials with similar assessments and participant burden (see the protocol for more details), it is estimated that a minimum of 60 participants (and up to 90) per site will be required. This will result in a total of 300-450 participants across the five clinical sites. With a sample size of 300, conservative assumptions about the impact of the propensity score weighting, and a type I error rate of 0.05, we will have 80% power to detect effect sizes that are at least as large as 0.23 for each environmental measure when they are modelled as continuous predictors. This represents the minimum change in the HD composite outcome that would be detected as statistically significant with 80% power for a 1-unit change in the

TPL/008/2(v1.0)

DOMINO-HD: STATISTICAL ANALYSIS PLAN

environmental measure, suggesting the study has reasonable power for small to moderate effects.

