5.3 RECRUITMENT

Participants will be recruited from five current Enroll-HD sites across Europe. Up to 90 participants will be recruited from each site (minimum of 60).

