We will derive a Mediterranean Diet Index (MDI) as defined by (Trichopoulou et al., 2003). This index's values range from 0 to 9, with higher values indicating higher adherence to an MD. The final score is the sum of nine elements, each of which is either 0 or 1. Beneficial components (namely 1. vegetables, 2. legumes, 3. fruits and nuts, 4. cereal, and 5. fish) contribute one point if their consumption is above the sex-specific sample median. For non-beneficial components, (6. dairy, 7. meat and poultry) one point is assigned to those whose consumption is below the sex-specific sample median. Finally, for alcohol consumption (8.), one point is assigned to men who consume between 10 and 50 g per day and to women who consume between 5 and 25 g a day. Finally, to score lipid intake, the unsaturated to saturated fatty acids (9.) ratio is calculated and one point assigned if the ratio exceeds the sex-specific sample median. A full description of the definition of the MDI is in Appendix A.

Additionally, the Healthy Eating Index (HEI) will be used as a diet score. Its values range from 0 to 100, with higher values representing better eating habits. The final score is a sum of 13 components, nine categories of adequate eating, and four moderators. A full description of the definition of the HEI is in Appendix B.

Both MDI and HEI will be used (one at a time) to assess the sensitivity of our findings. Additionally, the two scores will be compared as to their effect on the progression of HD – unless one is dropped (see section 6.2.3).

3. Physical activity:

Step counts over a 6-week period from the baseline assessment will be extracted from each participant's FitBit. 5000 steps per day (Tudor-Locke et al., 2013) will be used as a threshold to dichotomise participants into sedentary (< 5000 steps per day) and active (\geq 5000 steps per day).

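### Site is pre-specified in none of the lifestyle-effect models, so differences between the five sites could be attributed to sleep, diet or physical activity

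*SAP*

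**What the plan says.** Section 5.3: "Participants will be recruited from five current Enroll-HD sites across Europe". Section 6.2.1 sets the aim: "The impact of each lifestyle factor of interest (namely sleep, diet, physical activity) will be estimated as a causal treatment effect".

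The covariates are then given model by model:

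- **Weighted analysis (6.2.1).** "The covariates which will be used to control for confounding bias are the lifestyle factors not under study in each case", together with baseline cUHDRS. Then: "If sample size allows, additional covariates will be added to control for confounding bias, including age and HD stage". This last list is open, but site is not named in it. Section 6.2.2 gives the optional set as age, HD stage and baseline outcome only.
- **Fallback if balance fails (6.2.1).** Mean differences, and/or a regression on the other two lifestyle factors, age and HD stage. Baseline outcome is not in this list.
- **Unweighted regression (6.2.2).** "Unweighted analyses (using regression models) will control for age, HD stage, as well as baseline values for the outcomes", plus the other two lifestyle factors in continuous form.
- **LifeHD (Appendix C, Step 1).** Age, sex, HD stage, time since diagnosis and follow-up time.

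Site is used in four places, all descriptive: participant flow (5.2), withdrawal (5.4.4), baseline tables (5.5.2) and missing outcome data (6.3). The SAP has no random site effect, no clustered standard error and no sensitivity analysis by site.

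The beneficial food groups of the Mediterranean Diet Index (MDI) "contribute one point if their consumption is above the sex-specific sample median" (6.2). The median is taken within sex but pooled over sites.

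**The concern.** Site confounds a lifestyle contrast if it is related both to exposure group and to the 12-month outcome given the other covariates.

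**Exposure.** No cut-point in the SAP is site-specific. With a pooled median, a site whose usual diet is closer to the Mediterranean pattern contributes more high scorers, and the diet contrast becomes partly a contrast between sites.

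**Outcome.** cUHDRS combines two rated scales (TFC, TMS) with two cognitive tests, one of them word reading. Raters, test language and local care could plausibly differ by site. Adjusting for baseline removes much of a stable shift but not site-specific change over 12 months.

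Sections 6.2.3 and 6.2.5 plan OVtool or E-values for unobserved confounders. Site is observed and can simply be modelled. At stake are the validity of the tests and intervals for effects that the SAP labels causal.

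**Working it through.** **1. The plan's own figure.** Section 3.3 takes 300 participants, a 5% test and a cautious but unquantified allowance for weighting. Its conclusion reads: "we will have 80% power to detect effect sizes that are at least as large as 0.23 for each environmental measure". For a slope per SD of the predictor, two-sided 5% (sidedness is not stated), the detectable effect is (1.960 + 0.842)/√300 = 0.162 without a weighting penalty. The stated 0.23 needs an effective sample of (2.802/0.23)² ≈ 148, a design effect of 300/148 ≈ 2.02. The SAP gives no design effect, so 0.23 is compatible with a halved effective sample but cannot be confirmed. The point about site does not depend on it.

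**2. What drives the error.** Assume 5 sites of n = 60 (N = 300), no true effect, a baseline-adjusted regression and residual SD 1. Let p_s be the exposure prevalence at site s, p̄ its mean, and τ the SD of the site shift in the 12-month score. Leaving site out adds an error to the estimate with SD

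τ · n · √Σ(p_s − p̄)² / [N p̄(1 − p̄)].

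This is zero if either τ or the spread of p_s is zero. Example: prevalences 15, 25, 35, 45, 55% and τ = 0.3.

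- Σ(p_s − p̄)² = 2(0.20² + 0.10²) = 0.10, and N p̄(1 − p̄) = 300 × 0.35 × 0.65 = 68.25.
- Added SD = 0.3 × 60 × √0.10 / 68.25 = 0.083.
- Ordinary sampling SD = 1/√68.25 = 0.121.
- True SD ≈ √(0.121² + 0.083²) = 0.147.
- Reported SE ≈ √[(1 + 0.8 × 0.09)/68.25] = 0.125, where 0.8 = 4/5 is the part of τ² that falls in the pooled residual.
- Ratio ≈ 1.17, so the nominal 5% test rejects 2[1 − Φ(1.96/1.17)] ≈ 9.5%.

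**3. Simulation of the same set-up.** There were 3,000–4,000 runs per setting. Prevalences and τ are assumptions. Ranges span the repeated sets of runs.

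| Prevalence across sites | τ = 0 | τ = 0.1 | τ = 0.2 | τ = 0.3 |
|---|---|---|---|---|
| 25–42% | – | – | – | 5.2% |
| 15–55% | 4.9% | 5.1–5.8% | 6.7–7.4% | 9.5–10.8% |
| 10–65% | 4.7% | 5.7–5.8% | 9.5–9.7% | 14.3–15.8% |

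With equal prevalence, rejection is about 5%. With four site indicators it is 4.4–5.8% throughout.

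**4. A different set-up.** Here exposure is split at the pooled median, the baseline correlation is 0.9, and site explains an assumed share of exposure variance and of outcome variance.

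- Baseline-adjusted, site share of residual outcome variance 10%: rejection is 7.4%, 8.8% and 10.6% at exposure shares of 5%, 10% and 20%.
- Unadjusted mean difference, site share of outcome variance 10%: 7.9%, 8.4% and 10.9%.
- With site indicators: 4.7–5.4% in these settings.

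Monte Carlo error is about 1 point. For the mean difference the relevant share is that of the whole follow-up score, including stable site differences that baseline adjustment would largely remove. The 6.2.1 fallback is therefore the more exposed.

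**5. Cost of adding site.** In the simulations the SE rose from 0.126 to 0.134 (6%) and from 0.127 to 0.142 (12%); other runs gave 2–8%. On the scale of section 3.3, if site explains 10%, 20% or 30% of exposure variance, 0.23/√(1 − share) gives 0.242, 0.257 or 0.275.

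**6. Site in the weights.** Section 6.1.1 cites 60–80 observations per covariate per group. Three core covariates plus four site indicators make seven: 7 × 60 = 420 to 7 × 80 = 560 per group, against 300–450 participants in total.

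**The case against.** **Site is not excluded.** This stands: the optional list in 6.2.1 is open. But the lists in 6.2.2 and Appendix C are closed, and nothing pre-specifies site. The fair criticism is omission, not prohibition.

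**The site differences are conjecture.** This stands. The SAP documents no differences in diet, raters or test language between sites. A reader might infer that such differences are established; they are plausible mechanisms only.

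**The inflation needs strong inputs.** This also stands. A reader might infer that intervals are too narrow whenever exposure prevalence differs by site. They are not: with no residual site shift, rejection stays near 5% even at 10–65% prevalence, and with prevalence of 25–42% it is 5.2% at τ = 0.3.

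**Only the MDI uses pooled medians.** This is partly right. The Healthy Eating Index (HEI) has fixed standards and a cut-off of 59, with the median as fallback, and step count has a fixed 5000 threshold. But a fixed threshold does not equalise prevalence across sites, and the sleep and MET cut-points are sample quantiles.

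**The SMS sub-study omits site too.** A reader might extend the point to section 6.4. That comparison is randomised and its covariate list is open, so omitting site there affects precision only and cannot create a lifestyle effect.

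**The analyses are exploratory.** The primary objective is feasibility, cUHDRS effects are secondary, and 4.1.1 calls the study exploratory. This limits the weight of the point, but the effects are still to be presented as causal, with 5% tests and 95% intervals.

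**Conclusion.** The point holds as an omission worth correcting. Site is tabulated but pre-specified in none of the weighted, fallback, unweighted or LifeHD models, although effects are to be read as causal across five sites.

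The consequence is conditional. Under assumed inputs, false-positive rates of about 7–16% arise when exposure prevalence varies widely (15–55% or 10–65%) and a site shift of 0.2–0.3 residual SD remains after baseline adjustment. They are near 5% when either source of variation is absent or small. The actual size cannot be known from the SAP. That the omission exists is certain; that it will materially distort the results is not. A reader might also infer that site must enter the propensity weights, but the SAP's own sample-size guidance makes that infeasible at 300–450 participants.

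**What to change.** In sections 6.2.1 and 6.2.2 and Appendix C, state that site enters as a fixed effect (four indicators) in:

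- the outcome part of the doubly robust model;
- the unweighted and fallback regressions;
- the regressions that build LifeHD and those that use it.

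A plain mean difference cannot carry site, so where one is reported under the fallback it should be accompanied by the site-adjusted regression. For each binary exposure, report prevalence and weighted balance by site. Do not require site in the propensity weights, and leave the SMS sub-study as it is.

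The cost is SAP wording and four parameters per model; no new data are needed. If exposure differs strongly by site, the standard error rises by roughly 2–12%, because between-site information is no longer used. If exposure does not differ by site, there is essentially no loss.

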4. STATISTICAL PRINCIPLES

4.1 LEVELS OF CONFIDENCE AND P-VALUES

95% confidence intervals will be reported. All p-values will be compared to 5% level of significance.

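### If balance is not reached (maximum KS above 0.1), section 6.2.1 lets an unadjusted mean difference stand as the effect of a lifestyle factor and leaves baseline outcome out of the fallback regression, in conflict with section 6.2.2

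*SAP*

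**What the plan says.** SAP section 6.2.1 plans a doubly robust, propensity-weighted estimate of the effect of sleep, diet and physical activity, provided the maximum KS over the balancing covariates is at most 0.1. If that is not met, "then mean differences of the outcome will be reported, and/or estimates using a regression model adjusting for the other two lifestyle factors", together with age and HD stage, and without weights. Baseline outcome is not in this list, although the same section names baseline cUHDRS among the covariates to be balanced.

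Section 6.2.2 describes the same situation differently: "If we are unable to achieve adequate balance, then unweighted regression and means difference will be reported". It says that unweighted regressions adjust for age, HD stage, baseline outcome and the continuous versions of the two remaining lifestyle factors. It also asks for significance tests of the outcome mean difference between the exposure groups.

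Section 4.1 adds: "All p-values will be compared to 5% level of significance". The only design-stage error rate is in section 3.3, which rests on "conservative assumptions about the impact of the propensity score weighting, and a type I error rate of 0.05".

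**The concern.** The two sections disagree on two things that change the result: whether the raw difference may be the only estimate (6.2.1) or comes with a regression (6.2.2), and whether the fallback regression includes baseline outcome. Neither says which fallback estimate carries the inference.

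The stated aim is a causal effect with confounding controlled. A raw difference controls nothing, and it becomes available when the balance check has failed. If people who sleep or move less are already more severely affected, their raw 12-month cUHDRS differs even when the factor has no effect. That difference could be reported, with a p-value judged at 5%, as the effect of the factor.

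**Working it through.** **The plan's own figure.** Section 3.3 gives a detectable effect of 0.23 at N=300, 80% power and error rate 0.05 (taken as two-sided).
- Without weighting loss: (1.960 + 0.842)/√300 = 0.162.
- To reach 0.23: effective N = (2.802/0.23)² ≈ 148, a design effect of 300/148 ≈ 2.0.

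The SAP does not quantify the weighting loss, so 0.23 can be neither confirmed nor refuted. It applies to exposures "when they are modelled as continuous predictors" and gives no error rate for the balance check followed by a fallback.

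**Raw difference by hand.** Inputs from the SAP: N=300 and a first-tertile split (100 v 200). Assumptions: normal variables, baseline to 12-month correlation 0.9, exposure-severity correlation r.
- Mean gap in a normal exposure between the upper two thirds and the lowest third: 0.3636 × (3 + 1.5) = 1.636 SD.
- Bias of the 12-month difference: 1.636 × r × 0.9 = 0.147, 0.295 and 0.442 SD for r = 0.1, 0.2 and 0.3.
- SE = √(1/100 + 1/200) = 0.1225. Two-sided rejection at 5%: 22.5%, 67.2% and 95.0%.
- For change, SD = √(2 × 0.1) = 0.447 and bias = 1.636 × r × 0.1/0.447 = 0.037, 0.073 and 0.110 SD. Rejection: 6.0%, 9.2% and 14.6%.

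In simulation under these assumptions, with logistic ATE weights and three balancing covariates, balance failed in about 50 to 65% of samples. With half failing at r = 0.2, the whole procedure gives about 0.5 × 67.2 + 0.5 × 5 = 36%. With 60% failing at r = 0.3, it gives about 0.6 × 95.0 + 0.4 × 5 = 59%.

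**Simulation of the whole procedure**, no lifestyle effect, n=300, logistic ATE weights, doubly robust model if KS ≤ 0.1. Set-up A: all pairwise correlations equal to r, 2000 runs per cell. Set-up B: exposure-lifestyle correlation 0.2, baseline to 12-month correlation 0.9, 600 runs per cell. False positives in %:

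| Fallback, outcome | r=0 | 0.1 | 0.2 | 0.3 |
|---|---|---|---|---|
| B: raw difference, 12-month value | 6 | 15 | 36 | 62 |
| A: raw difference, 12-month value | 6.0 | 14.3 | 43.6 | 69.9 |
| A: raw difference, change | 5.4 | 7.8 | 14.8 | 34.4 |
| A: baseline-adjusted regression, 12-month value | 5.9 | 4.2 | 5.0 | 4.8 |
| A: baseline-adjusted regression, change | 5.3 | 5.6 | 4.6 | 4.4 |

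In set-up B the raw-difference fallback gave about 5 to 11% for change over r = 0.1 to 0.3, and balance check then baseline-adjusted regression gave 5 to 6%. Over all 20 cells of set-up A (n=300 and 210, r from 0 to 0.4, both outcomes) the regression fallback gave 4.2 to 6.2%.

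**Leaving baseline out, as 6.2.1 does.** Age and a four-level stage were added to the regression, with assumed correlations with severity of 0.4, and 0.8 before categorising. The whole procedure then gave 8, 20 and 38% at r = 0.1, 0.2 and 0.3. With baseline included it gave 4.7 to 5.8%.

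**How often the fallback is used.** In set-up A at n=300, balance failed in about 40% of samples with no confounding and in 82 to 84% at r = 0.4. At n=210 (70% follow-up of 300, the feasibility cut-off in 6.1.1) it failed in 76 to 96%.

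**The case against.** **The weights.** A reader might infer that discarding the weights when KS exceeds 0.1 is itself the error. The documents do not support this. The unweighted regression in 6.2.2 includes baseline outcome and keeps the error rate near 5%. Reporting a doubly robust estimate despite failed balance is a preference, not a requirement.

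**The figures.** A reader might take rates such as 36% or 62% as the error rate of the plan. They belong to one permitted reading, the raw difference as the inferential result; under 6.2.2 an adjusted estimate is always reported. They also rest on logistic weights, whereas section 6.6 names twang, CBPS and entbal. With entropy balancing on three moments, balance was reached in 61 to 72% of samples at n=300, and in 79 to 86% if either ATE or ATT may be chosen. In the entropy-balancing runs the raw fallback gave 9, 28 and 42% at n=300 for r = 0.1, 0.2 and 0.3, and 8, 9 and 13% at n=450. The SAP gives no exposure-severity correlation, and at zero there is no inflation. These points limit the size but do not remove the problem.

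**The 0.05 in section 3.3.** It is an input to a power statement, not a promise about every p-value.

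**Context.** The primary objective is feasibility, and section 4.1.1 calls the study exploratory. The SAP also plans overlap checks, possible trimming, and OVtool or E-values, including for unweighted analyses. This lowers the priority. It does not justify presenting a confounded contrast as the effect of a lifestyle factor, nor does it settle which of the two sections applies.

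**Conclusion.** The point holds for two items: the raw mean difference as a possible sole result, and the missing baseline outcome in the fallback regression of 6.2.1. Both conflict with 6.2.2. The test of the raw outcome difference in 6.2.2, judged at 5%, adds to the first.

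The size depends on confounding that the SAP does not quantify. At n=300 with logistic weights and exposure-severity correlations of 0.1 to 0.3, the raw-difference option gives about 15 to 62% false positives for the 12-month value. For change it gives about 5 to 11%, or 8 to 34% when all pairwise correlations are equal. Neither the KS limit nor the loss of the weights causes the inflation. The feasibility criteria in 6.1.1 are unaffected. This should be fixed before analysis but does not threaten the primary objective.

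**What to change.** In sections 6.2.1 and 6.2.2 use one rule: *If the maximum KS exceeds 0.1, the single inferential estimate is the unweighted regression adjusting for the two remaining lifestyle factors (continuous), age, HD stage and the baseline value of the outcome. Unadjusted outcome mean differences are descriptive and carry no p-value.*

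Replace the and/or in 6.2.1 accordingly, add baseline outcome to its list, and remove the outcome from the significance tests of mean differences in 6.2.2. The doubly robust estimate may be shown alongside as a sensitivity analysis, flagged as not meeting the balance criterion and with its residual KS. Keep KS ≤ 0.1 as the feasibility criterion in 6.1.1.

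The cost is a change of wording and slightly more reporting. No new data are needed, and 6.2.2 already plans the regression.
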